**Table 4 Calculation of CDR Computerized Assessment System Domain Scores**

Name	Abbreviation	Unit	Calculation
Power of Attention	POW_ATT	ms	SRTM+VIGRT+CRTM
Continuity of Attention	CONT_ATT	#	(VIGACC*0.45)+(CRTACC*0.5)-VIGFA
Cognitive Reaction Time	COGRT	ms	CRTM-SRTM
Response Variability	POWATTCV	%	(SRTSD/SRT*100)+(CRTSD/CRT*100)+(VIGSD/VIGRT*100)
Quality of Working Memory	QL_WORK	SI	SPMSI+NWMSI
Quality of Episodic Secondary Memory	QL_EPIS	#	(DRECOACC+DRECNACC-100)+(DPICOACC+DPICNACC-100)+((IRCL-IRCLERR)*100/12)+((DRCL-DRCLERR)*100/12)
Speed of Memory	SPEEDMEM	ms	SPMRTM+NWMRTM+DRECRMTM+DPICRTM

Based on the derived domain scores, a standardized z-score will be derived for each CDR system domain using the formula below:

$$\text{Domain z-score} = (X_2 - X_1)/SD_1$$

Where:

$X_2$  is the domain score for each individual at any study assessment time post Baseline

$X_1$  is the Baseline domain score for that individual

$SD_1$  is the domain standard deviation of the population at Baseline

A composite z-score for the 7 CDR domains will be calculated based on the individual domain scores as:

(Continuity of Attention z-score + Quality of Episodic Secondary Memory z-score - Response Variability z-score + Quality of Working Memory z-score - Power of Attention z-score - Cognitive Reaction Time - Speed of Memory z-score)/7

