**Table 13: Calculation of CDR Computerized Assessment System Domain Scores (Study RVT-101-2001)**

Name	Abbreviation	Unit	Calculation	Interpretation
Power of Attention	POW-ATT	ms	SRTM+VIGRT+CRTM	Lower scores are better
Continuity of Attention	CONT-ATT	#	(VIGACC*0.45)+(CRTACC*0.5)-VIGFA	Higher scores are better
Cognitive Reaction Time	COGRT	ms	CRTM-SRTM	Lower scores are better
Response Variability	POWATTCV	%	(SRTSD/SRT*100)+(CRTSD/CRT*100)+(VIGSD/VIGRT*100)	Lower scores are better
Quality of Working Memory	QL-WORK	SI	SPMSI+NWMSI	Higher scores are better
Quality of Episodic Secondary Memory	QL-EPIS	#	(DRECOACC+DRECNACC-100)+(DPICOACC+DPICNACC-100)+((IRCL-IRCLERR)*100/12)+ ((DRCL-DRCLERR)*100/12)	Higher scores are better
Speed of Memory	SPEEDMEM	ms	SPMRTM+NWMRTM+DRECRTM+DPICRTM	Lower scores are better

Based on the derived domain scores, a standardized z-score will be derived for each CDR system domain using the formula below:

$$\text{Domain z-score} = (X2 - X1)/SD1$$

Where:

X2 is the domain score for each individual at any study assessment time post Baseline

X1 is the Baseline domain score for that individual

SD1 is the domain standard deviation of the population at Baseline

A composite z-score for the 7 CDR domains will be calculated based on the individual domain scores as:

$$(\text{Continuity of Attention z-score} + \text{Quality of Episodic Secondary Memory z-score} - \text{Response Variability z-score} + \text{Quality of Working Memory z-score} - \text{Power of Attention z-score} - \text{Cognitive Reaction Time} - \text{Speed of Memory z-score})/7$$

Missing data will be handled as follows:

- If any individual item (variable) is missing for a Domain Score, the Domain Score will be set to missing. Thus, no imputation of individual Domain Scores will be performed; all variables are needed in order to calculate each Domain Score.
- If a single Domain Score is missing for the derivation of the Composite score (ie, one of the 7 Domain Scores is missing), the average of the 6 non-missing Domain z-scores will be used to replace the missing Domain z-score.
- If >1 Domain Scores are missing, the Composite score will be set to missing.

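### SAP 5.13 fills a missing CDR domain with an average of z-scores that have not been sign-aligned, so the imputed value is generally wrong and, when the domains move together, is zero or has the wrong sign

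*SAP*

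**What the plan says.** SAP section 5.13 states that "a standardized z-score will be derived for each CDR system domain using the formula below": the post-baseline score minus that subject's baseline score, over the baseline SD. No domain is reversed at this step.

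Table 13 of the SAP labels three domains "Higher scores are better" (Continuity of Attention, Quality of Working Memory, Quality of Episodic Secondary Memory). It labels four "Lower scores are better" (Power of Attention, Cognitive Reaction Time, Response Variability, Speed of Memory). The composite adds the first three, subtracts the other four and divides by 7. Protocol Table 4 has the same formula, ending "Power of Attention z-score - Cognitive Reaction Time - Speed of Memory z-score)/7".

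Three missing-data rules follow in the SAP:

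- "If any individual item (variable) is missing for a Domain Score, the Domain Score will be set to missing".
- With exactly one domain missing, "the average of the 6 non-missing Domain z-scores will be used to replace the missing Domain z-score".
- With two or more domains missing there is no replacement, and no composite is calculated for that visit.

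The protocol has no missing-domain rule, and SAP section 7.3 gives the SAP precedence where the two differ.

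**The concern.** The replacement rule uses the defined term, Domain z-score, which is the unaligned quantity. Among six raw z-scores, improvement is positive in some and negative in others, so a subject who improves everywhere has values that cancel. The result then enters the composite formula as if it were an ordinary score for the missing domain. Neither document says that signs are aligned before averaging.

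The composite is a tertiary endpoint, collected at Weeks 4, 8, 12, 18 and 24 and analysed by MMRM and Wilcoxon test (SAP section 9.4.2), so affected records can enter at any of five visits. There is also a reproducibility problem. One programmer may follow the text and another may align signs silently, and their composites would differ.

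**Working it through.** **Inputs.** The z-score definition, direction labels, composite formula and missing-data rules are all in SAP 5.13. The plan gives no numerical figure to reproduce. The common improvement d is an assumption, and the ratios below do not depend on it. Call the three higher-is-better domains *accuracy* and the four lower-is-better domains *timing*.

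**1. Complete data.** Raw z is +d in three domains and -d in four. Composite = [3d - 4(-d)]/7 = 7d/7 = d. The formula's signs are coherent, so the fault is not there.

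**2. One accuracy domain missing.** The other six are two at +d and four at -d. Imputed value = (2d - 4d)/6 = -d/3, which is the wrong sign because it enters with a plus. Composite = (6d - d/3)/7 = 17d/21 = 0.810d, a 19.0% loss. At d = 0.50: imputed -0.167, composite 0.405.

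**3. One timing domain missing.** The other six are three at +d and three at -d. Imputed value = 0. Composite = 6d/7 = 0.857d, a 14.3% loss. At d = 0.50: composite 0.429.

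Equal worsening mirrors both cases, so the pull is toward zero change from baseline.

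**4. General form.** Let P and N be the sums of aligned z-scores (higher = better) over the available accuracy and timing domains. The raw average is (P - N)/6. The sign-aligned composite is (P + N)/6, which equals [P + N + (P + N)/6]/7.

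- Accuracy domain missing: literal minus aligned = [(P - N)/6 - (P + N)/6]/7 = -N/21.
- Timing domain missing: literal minus aligned = [-(P - N)/6 - (P + N)/6]/7 = -P/21.

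The literal rule therefore agrees with the aligned one only when the oppositely oriented domains sum to zero.

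**5. Unequal patterns, Quality of Episodic Secondary Memory missing** (aligned changes, assumed):

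| Accuracy | Timing | Imputed | Literal composite | Aligned composite | Complete data |
|---|---|---|---|---|---|
| +0.3 | +0.3 | -0.100 | 0.243 | 0.300 | 0.300 |
| 0 | +0.3 | -0.200 | 0.143 | 0.200 | 0.171 |
| +0.3 | 0 | +0.100 | 0.100 | 0.100 | 0.129 |
| -0.3 | +0.3 | -0.300 | 0.043 | 0.100 | 0.043 |
| +0.5 | -0.1 | +0.233 | 0.119 | 0.100 | 0.157 |

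In a subject-level simulation (d = 0.3, change SD 0.7, between-domain correlation 0 to 0.6, all assumed), the imputed value had the wrong sign in about 64-65% of subjects with an accuracy domain missing. With a timing domain missing it did so in about 50%.

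**6. When the rule is triggered.** Tracing tasks through Table 13:

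| Whole task lost | Domains lost |
|---|---|
| Immediate or Delayed Word Recall | 1 (Quality of Episodic Secondary Memory) |
| Simple Reaction Time | 3 |
| Digit Vigilance | 3 |
| Choice Reaction Time | 4 |
| Spatial or Numeric Working Memory | 2 |
| Word or Picture Recognition | 2 |

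Loss of any task other than word recall sets the composite to missing. The likeliest trigger is therefore the case in step 2. The case in step 3 needs an isolated missing variable.

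**7. Trial level.** Loss = share of subjects with exactly one domain missing × 1/7 (timing) or × 4/21 (accuracy), under a common shift. The share is not in the documents. Assumed 5%: 0.7% to 1.0%. Assumed 10%: 1.4% to 1.9%. Assumed 20%: 2.9% to 3.8%.

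**The case against.** The strongest reply is that this is a small matter of wording. The rule applies to the derivation of the composite, and a sensible programmer would align first. The formula is itself loosely written: "Power of Attention z-score - Cognitive Reaction Time - Speed of Memory z-score" drops the word z-score after Cognitive Reaction Time, and everyone will read that charitably. The trigger is narrow (step 6). Exclusion criterion 20 keeps out subjects who cannot complete the battery, and testing may be rescheduled within the visit window. The endpoint is tertiary and outside the testing hierarchy in SAP 7.5. All seven domains are also analysed separately as actual scores, without imputation.

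Most of this stands as a limit on consequence, but it does not make the rule right. Domain z-score is defined one way in that section, and code that aligned first would depart from the written text.

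A reader might also infer more than the documents support:

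- *That the imputed value is always zero or wrong-signed.* That is exact only for a common shift. In the third row of the step 5 table the sign is right and the two rules agree. In the fourth, the literal rule happens to recover the complete-data value and the aligned rule does not.
- *That the bias is toward no treatment effect.* Under a common shift the pull is toward zero change from baseline, which is different. Suppose both arms worsen by 0.30 with no true difference, and Quality of Episodic Secondary Memory is missing in 20% on active and 5% on placebo. The active arm then looks better by 0.30 × (0.20 - 0.05) × 4/21 = 0.009. The direction depends on missingness by arm.
- *That Protocol Table 4 shares the fault.* It holds only the formula, whose signs are correct.
- *That the CDR plus COWAT composite is certainly affected.* It uses the same domains, but no formula or missing-domain rule is given for it.

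**Conclusion.** The rule is wrong as written. It averages z-scores that point in opposite directions and uses the result as a domain score. Under a common shift, an affected subject-visit has a composite of 0.81d (accuracy domain missing, the likelier case) or 0.86d (timing domain missing) instead of d. In general the departure from the sign-aligned composite is -N/21 or -P/21, which can be zero or change sign.

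The 14% to 19% loss applies to a subject-visit with exactly one domain missing, not to the trial result. At trial level it is about 0.7% to 3.8% for assumed shares of 5% to 20%. No sign can be given for the effect on the treatment difference without knowing missingness by arm. The primary and secondary endpoints are untouched. The point is worth correcting because the rule is plainly unintended and cheap to repair.

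**What to change.** In SAP 5.13, state that the z-scores of Power of Attention, Cognitive Reaction Time, Response Variability and Speed of Memory are multiplied by -1 before any averaging. With one domain missing, the composite is then the mean of the six available sign-aligned z-scores. The rule for two or more missing domains stays as it is.

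Under a common shift this returns d whichever domain is missing. Like any fill from the other domains, it remains an approximation when domains diverge. Complete-data composites do not change. The cost is one sentence and a line of code, to be settled before unblinding, in keeping with SAP section 2. The same sentence can say whether the rule carries over to the CDR plus COWAT composite.

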## 6. SAMPLE SIZE CONSIDERATIONS

The sample size is based on assumptions of treatment benefit for one primary endpoint, the UPDRS- III total score. A sample size of 70 subjects per treatment group will allow a treatment difference of 4 points between placebo and active treatment in the change from baseline in UPDRS- III score to be detected with 88% power and a 0.05 significance level assuming an underlying standard deviation (SD) of 7.5

There are two secondary endpoints:

- ADAS-Cog 11 total score. A sample size of 80 subjects per treatment group will allow a treatment difference of 3 points between placebo and active treatment in the change from baseline in ADAS-Cog-11 score to be detected with 88% power and a 0.05 significance level assuming an underlying standard deviation (SD) of 6. Under the assumptions of a 2.5, 2.0 and 1.5 point treatment effect, the power is 74%, 55% and 35%, respectively.
- CIBIC+. A sample size of 80 subjects per treatment group will allow a treatment difference of 0.5 points between placebo and active treatment in the observed values in the CIBIC+ to be detected with 91% power and a 0.05 significance level assuming an underlying standard deviation (SD) of 0.95. Under the assumptions of a 0.4 and 0.3 point treatment effect, the power is 75% and 51%, respectively.

Randomization will be stratified according to Baseline MMSE score in the groupings of 14-17 points, 18-21 points and 22-26 points and according to whether subjects are or are not taking a cholinesterase inhibitor as a concomitant medication.

## 7. GENERAL CONSIDERATIONS FOR DATA ANALYSES AND HANDLING

The primary statistical framework will be to test the superiority of Intepirdine over placebo. The null hypothesis is as follows, with a significance level of  $\leq 0.05$  needed for the null hypothesis to be rejected.

- There is **NO** statistically significant difference between Intepirdine and placebo in the mean change from baseline to Week 24 in the UPDRS- III.
- There **IS** a statistically significant difference between Intepirdine and placebo in in the mean change from baseline to Week 24 in the UPDRS- III.

The individual Intepirdine arms will be tested, as follows:

- Intepirdine 70 mg vs placebo
- Intepirdine 35 mg vs placebo

All hypothesis tests will be 2-sided, performed at the 5% level of significance.

The primary endpoint needs to achieve a significance level of 0.05 within an Intepirdine dose to allow for testing of the secondary endpoints within that dose.

### 7.1. Interim Analyses

No formal efficacy interim analyses are planned. An external SMC will review the safety data on an ongoing basis. Internal reviews of interim blinded safety data (by the Sponsor medical monitor) will occur on a regular basis.

### 7.2. Final Analysis

There is only one analysis planned for this study. This final analysis will be performed upon completion of the following items:

- The database has been locked according to the study data management plan.
- The list of patients excluded from Per Protocol population has been identified.
- The study database is un-blinded.

### 7.3. General Table and Individual Subject Data Listing Considerations

Tables, listings and figures will be prepared in accordance with the current International Conference on Harmonization Guidelines. The information and explanatory notes in the “footer” or bottom of each table and listing will include the following information:

- Date of output generation
- SAS® program name, including the path that generates the output
- Any other output specific details that require further elaboration

All hypothesis tests and confidence intervals will be two-sided at an alpha level of 5%.

Version 9.1 or higher of the SAS system will be used to analyze the data as well as to generate tables, figures, and listings.

In general, tables will be formatted with a column displaying findings for all subjects combined. The summary tables will clearly indicate the number of subjects to which the data apply, and “unknown” or “not performed” will be distinguished from “missing” values data.

The treatment groups will be referred to in the tables, listings, and figures with the following conventions (and in this order, left to right, in the tables):

- Placebo
- Intepirdine 35 mg
- Intepirdine 70 mg
- Total (all 3 treatment groups combined)

For the primary efficacy and secondary efficacy variables ONLY, a table will be presented that will compare the POOLED data (pooled across the 35 mg and 70 mg Intepirdine arms) vs placebo.

Data analyses will be performed by, or under the direct supervision of, Axovant Sciences. Listings will be sorted by subject, period and time, or as appropriate. Tabulations will be presented by treatment and time. Unless stated otherwise, descriptive summaries will include n, mean, standard deviation, median, minimum, and maximum for continuous variables, and n and percent for categorical variables.

The geometric mean with associated 95% CI, between-subject CVs (CVb), and SD of the logs based on the geometric mean, will be included for the log-transformed PK parameters. The between-subject %CV of the log transformed variable will be calculated as:

- $\%CVb = 100 * \sqrt{(e^{SD^2} - 1)}$ , with SD of the log-transformed data

Deviations from the analyses as described in this SAP will be identified in the final Clinical Study Report. When differences exist between the protocol-described analysis and the SAP, the SAP will take precedence.

All data collected in the CRF, as well as external vendor data, will be provided in data listings, sorted (in general) by patient and date. For date fields, Study Day will be calculated and presented in these listings.

#### **7.4. Analysis Populations**

It is intended that a complete accounting of patients for the analysis populations will be provided, from the Screening Population through the Per-Protocol Population.

- Screening Population: All patients who are screened (signed an informed consent) will be included in the Screening Population.
- Placebo Run-In Population: All patients who took at least 1 dose of IP in the Placebo Run-in will be included in the Placebo Run-In Population. This population will be used to provide an accounting of the disposition of patients during this phase of the study.

- Randomized Population: The Randomized Population will include all patients who are randomized.
- Safety Population: All subjects who were randomized and took at least one dose of double-blind investigational product.
- Intent-to-Treat (ITT) Population: All subjects randomized to treatment who have taken at least one dose of double-blind investigational product and who have a baseline and at least one post baseline primary efficacy assessment for the UPDRS-III **or** for the ADAS-Cog 11. This will be the primary population used for the efficacy analysis of all variables EXCEPT the UPDRS Part III and Part 5.
- UPDRS Primary Analysis Population: This will be the primary population used for the UPDRS Part III efficacy analysis, and is comprised of all ITT patients EXCLUDING those with no change OR a worsening in UPDRS-III total score prior to a dose increase in anti-parkinsonian medication (including but not limited to L-dopa, dopamine agonists, and monoamine oxidase inhibitors) and where there is *subsequent* improvement or stabilization of UPDRS-III total score.
  - Dose increase in anti-parkinsonian medication is defined as an increase in dose, dose frequency or commencement of anti-parkinsonian medication where the total daily dose of anti-parkinsonian medication at Week 24 is higher than at Baseline.
- UPDRS Sensitivity Analysis Population: All ITT patients EXCLUDING those who increase or start anti-parkinsonian medication treatment during the double-blind treatment period.
  - Dose increase in anti-parkinsonian medication is defined as an increase in dose or frequency or commencement of anti-parkinsonian medication where the total daily dose of anti-parkinsonian medication at Week 24 is higher than at Baseline.
- Completers (CS) Population: ITT subjects who have completed the Week 24 visit with non-missing endpoints for all three variables, the UPDRS-III, ADAS-Cog 11, and CIBIC+. This population will be used for supportive analysis of all efficacy variables except the UPDRS variables.
- UPDRS Completers Primary Analysis Population: UPDRS Primary Analysis Population Patients who have a Week 24 UPDRS Part III value. This will be run only on the UPDRS Part III and Part 5 variables.
- Pharmacokinetics (PK) Population: All subjects in the Safety Population who undergo plasma PK sampling and have at least one post-baseline evaluable PK concentration result.
- Per-Protocol (PP) Population: Subjects in the ITT Population who have no major protocol violations. The PP Population will not be analyzed if this population comprises more than 95% or less than 50% of the ITT Population. This population will be used for confirmatory analysis all efficacy variables except the UPDRS variables. The PP Population will be identified prior to breaking the study blind. Major protocol violations will be defined as follows:
  - Subject had >7 consecutive days interruption in double-blind study medication

- Treatment with excluded concomitant medications during the double-blind treatment period.
  - If taking an acetylcholinesterase inhibitor, subject had a change in AChEI dose or frequency during the double-blind treatment period.
  - Significant study drug administration errors.
  - Invalid baseline primary or secondary efficacy assessment.
  - Subject does not have MMSE score 14-26 inclusive at Screening and Baseline
  - Subject's baseline MMSE declined by 4 or more points from Visit 2 (Run-in) to Baseline
  - Evidence of other causes of dementia other than DLB as the primary cause
  - History or presence of significant medical or psychiatric condition at Screening.
  - Subject does not live with (or have substantial Periods of contact with) a regular caregiver [at least 10 hours total and at least 3 days per week]).
  - Subject is <80 % compliant or > 120% compliant between Visit 11 (Week 18) and Visit 12 (Week 24) with study drug. Patients who fail to return their bottle (and thus compliance cannot be determined) will be assumed to have been compliant for purposes of the Per Protocol population.
- UPDRS Per-Protocol (PP) Population: Subjects in the UPDRS Sensitivity Population who have no major protocol violations. The PP Population will not be analyzed if this population comprises more than 95% or less than 50% of the ITT Population. This population will be used for confirmatory analysis of the primary efficacy variable, UPDRS Part III (and Part 5). The PP Population will be identified prior to breaking the study blind. Major protocol violations will be defined as follows:
    - Subject had >7 consecutive days interruption in double-blind study medication
    - Treatment with excluded concomitant medications during the double-blind treatment period.
    - If taking an acetylcholinesterase inhibitor, subject had a change in AChEI dose or frequency during the double-blind treatment period.
    - Significant study drug administration errors.
    - Invalid baseline primary or secondary efficacy assessment.
    - Subject does not have MMSE score 14-26 inclusive at Screening and Baseline
    - Subject's baseline MMSE declined by 4 or more points from Visit 2 (Run-in) to Baseline
    - Evidence of other causes of dementia other than DLB as the primary cause
    - History or presence of significant medical or psychiatric condition at Screening.

- Subject does not live with (or have substantial Periods of contact with) a regular caregiver [at least 10 hours total and at least 3 days per week]).
- Subject is <80 % compliant or > 120% compliant between Visit 11 (Week 18) and Visit 12 (Week 24) with study drug. Patients who fail to return their bottle (and thus compliance cannot be determined) will be assumed to have been compliant for purposes of the Per Protocol population.

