### **10.3. Data Analysis Considerations**

#### **10.3.1. Analysis Populations**

It is intended that a complete accounting of patients for the analysis populations will be provided, from the Screening Population through the Per-Protocol Population.

- Screening Population: All patients who are screened (signed an informed consent) will be included in the Screening Population.
- Placebo Run-In Population: All patients who took at least 1 dose of IP in the Placebo Run-in will be included in the Placebo Run-In Population. This population will be used to provide an accounting of the disposition of patients during this phase of the study.
- Randomized Population: The Randomized Population will include all patients who are randomized.
- Safety Population: All subjects who were randomized and took at least one dose of double-blind investigational product.
- Intent-to-Treat (ITT): All subjects randomized to treatment who have taken at least one dose of double-blind IP and who have a baseline and at least one post-baseline efficacy assessment for the UPDRS-III *or* for the ADAS-Cog 11. This will be the primary population used for the efficacy analysis of all variables EXCEPT the UPDRS Part III and Part 5. In analyses using this population, subjects will be grouped according to their randomized treatments.
- UPDRS Primary Analysis Population: This will be the primary population used for the UPDRS Part III efficacy analysis, and is comprised of all ITT patients EXCLUDING those with no change OR a worsening in UPDRS-III total score prior to a dose increase in anti-parkinsonian medications and where there is *subsequent* improvement or stabilization of UPDRS-III total score.
  - Dose increase in anti-parkinsonian medication is defined as an increase in dose, dose frequency or commencement of the medication where the total daily dose of the medication at Week 24 is higher than at Baseline.
- UPDRS Sensitivity Analysis Population: All ITT patients EXCLUDING those who increase or start an anti-parkinsonian medication during the double-blind treatment period.
  - Dose increase in an anti-parkinsonian medication is defined as an increase in dose or frequency or commencement of the medication where the total daily dose of the medication at Week 24 is higher than at Baseline.
- Completers (CS) Population: ITT subjects who have completed the Week 24 visit with non-missing endpoints for all three variables, the UPDRS-III, ADAS-Cog 11,

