## 9. EFFICACY

### 9.1. General Considerations

Tabulation of the primary and secondary endpoints will generally be presented for the ITT, Per-Protocol, and Completers Population. The primary and secondary endpoints will be tabulated for the subgroups, while other variables may be added for subgroup analysis. Efficacy assessments will be performed on the observed cases dataset unless otherwise specified. The UPDRS Primary Analysis Population will form the basis for the primary conclusions regarding the primary efficacy variable (for the UPDRS Part III), while the ITT Population will form the basis for conclusions regarding all other endpoints. The UPDRS Part 5 will also be assessed using the UPDRS Primary Analysis Population.

Baseline or pre-dose assessment is the last available non-missing assessment prior to time of first dose of double-blind treatment, unless otherwise specified. If there are multiple efficacy assessments for a given parameter collected on the same date, the later of these assessments will be used.

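### The primary UPDRS-III population is defined by a post-randomisation medication increase and the later UPDRS-III score; for increases after Week 4 in patients not improved beforehand, the Week 24 primary outcome decides who is analysed.

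*SAP*

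**What the plan says.** SAP 7.4 and, in near-identical terms, Protocol 10.3.1 define a UPDRS Primary Analysis Population: "ITT patients EXCLUDING those with no change OR a worsening in UPDRS-III total score prior to a dose increase in anti-parkinsonian medication", where there is subsequent "improvement or stabilization of UPDRS-III total score". An increase counts only if the "total daily dose of anti-parkinsonian medication at Week 24 is higher than at Baseline". SAP 9.1 gives this set its role: "The UPDRS Primary Analysis Population will form the basis for the primary conclusions regarding the primary efficacy variable".

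The other relevant sets are:

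- ITT: dosed patients "who have a baseline and at least one post baseline primary efficacy assessment for the UPDRS-III" or for the ADAS-Cog 11. SAP 7.4 makes it primary for everything except the UPDRS variables.
- UPDRS Sensitivity: "All ITT patients EXCLUDING those who increase or start anti-parkinsonian medication treatment during the double-blind treatment period".
- UPDRS Completers: "UPDRS Primary Analysis Population Patients who have a Week 24 UPDRS Part III value".
- UPDRS Per-Protocol: built on the Sensitivity set.

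SAP 9.1 also says: "Tabulation of the primary and secondary endpoints will generally be presented for the ITT, Per-Protocol, and Completers Population".

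Table 2 in both documents marks UPDRS-III at Baseline, Week 1, Week 4, Week 24 and Visit 13. Visit 13 falls 14 to 19 days after Visit 12 and is only for patients not entering the extension. Early termination is not marked. SAP 9.3.2 names only Baseline, Week 4 and Week 24.

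**The concern.** The rule has two parts, and both use data from after randomisation. The first is the medication increase. The second is the score that follows it: a good later score removes the patient and a poor one keeps the patient in. The arms compared are then no longer the randomised arms, and for some patients the endpoint being tested decides whether they are counted.

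The rule also cannot be applied as written to everyone. Stabilisation has no threshold and no reference score. The increase is recognised only from the Week 24 dose, so a temporary increase does not count. A patient who increases after Week 4 and withdraws before Week 24 has neither a Week 24 dose nor a later UPDRS-III score, and so cannot be classified.

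At stake is the one primary analysis. Under SAP 7.5 it gates the 35 mg comparison and the secondary endpoints.

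**Working it through.** **1. The rule against the schedule.** Take a patient not improved before an increase made after Week 4. The next scheduled UPDRS-III is Week 24, the primary endpoint. Improved or stable means out; worse means in. Visit 13 comes later and covers only some patients, so it does not replace Week 24. For an increase between Weeks 1 and 4, the Week 4 score could serve. A patient who had improved before the increase stays in whatever Week 24 shows. This step needs no simulation.

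**2. The plan's own figure.** SAP 6: 70 per group, difference 4, SD 7.5, two-sided 0.05. Power = Φ(4 / (7.5 × √(2/70)) − 1.96) = Φ(3.155 − 1.96) = 88.4%. The stated 88% reproduces.

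**3. Illustrative size.** From the documents: effect 4 and SD 7.5. Assumed: placebo mean change 0, SD 7.5 at both visits, half the effect present at Week 4, Week 4–24 correlation 0.5, and an increase that lowers Week 24 by 6 points. Increases occur at the stated rates among patients no better than baseline at Week 4. The plan's exclusion is read as increase, Week 4 change ≥ 0 and Week 24 ≤ Week 4. Differences are placebo minus active.

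| Rate, placebo/active | Plan | All increasers dropped (Sensitivity set) | All observed ITT values | Post-increase values missing |
|---|---|---|---|---|
| 40%/20% | 3.71 | 3.57 | 3.27 | 4.00 |
| 30%/30% | 4.03 | 3.97 | 3.82 | 4.00 |
| 20%/40% | 4.34 | 4.35 | 4.35 | 4.00 |
| 10%/5% | 3.94 | 3.91 | 3.81 | 4.00 |

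The last column is 4.00 because missing at random holds by construction. The all-observed column answers a different question (treatment policy), so its distance from 4 is not bias.

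Check at 40%/20%: placebo increases are 0.50 × 0.40 = 20.0%; active, Φ(−2/7.5) × 0.20 = 0.395 × 0.20 = 7.9%. All observed values give 4 − 6 × (0.200 − 0.079) = 3.27, as tabulated.

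**4. Which part of the rule moves the estimate.** At 40%/20%, dropping every increaser moves 4.00 to 3.57. Putting back those who worsened, which is the score-based part, moves it to 3.71. The shift below 4 therefore comes from deletion on the event, and selection on the score offsets some of it. The rule removes 18.1% of placebo patients and keeps 1.9% who increased (80 × 0.019 ≈ 1.5 patients). At equal rates both parts are within 0.1 of nothing.

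**5. No drug effect.** At 30%/30%, rejection is about 5%. At 40%/20% the plan shifts by about −0.3, the Sensitivity set by −0.4 and all observed values by −0.6, all against the drug. Reversing the rates reverses the signs.

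**6. Different assumptions.** With a 5-point benefit, the full effect already at Week 4 and 30%/30%, the plan gives 3.98 to 4.04 (later change judged against Week 4 or Baseline), the Sensitivity set 3.90 and all ITT values 3.69.

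**7. Trigger not observed.** If the increase responds to an unrecorded score between Weeks 4 and 24 (assumed correlations 0.6 with Week 4 and 0.8 with Week 24), then at 40%/20% the plan gives 3.30 and the missing-value approach 3.53. Both fall short of 4.

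**The case against.** The strongest reply is about size and protection. The rule is pre-specified, and SAP 2 says decisions on the final analyses precede unblinding. The shifts are tenths of a point. In the first model at 40%/20% the plan lies nearer to 4 than either the Sensitivity set or all ITT values. The Sensitivity set is not selected on the score, so it does check that part of the rule, and an ITT tabulation is already foreseen. The assumed rates and the 6-point benefit are not anchored in the documents, and the Protocol Summary asks patients not to start additional DLB treatments, which may keep increases rare.

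Most of this stands, and it limits the claim. A reader might infer that the rule favours the drug, or that selection on the outcome produces a large bias. The documents support neither: the direction depends on unstated rates, and in these runs selection on the score is the smaller part.

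It does not remove the defect. Fixing a rule in advance does not undo selection on the outcome. Blind identification is stated for the Per-Protocol sets, and SAP 7.2 asks for a list only for Per-Protocol. The Sensitivity set still deletes on a post-randomisation event, Completers inherits the primary set, Per-Protocol inherits the Sensitivity set, and the ITT tabulation is only generally planned.

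**Conclusion.** The structural point holds with high confidence: the primary UPDRS-III set depends on a post-randomisation event and, for increases after Week 4 in patients not improved beforehand, on the primary outcome. The rule is also undefined for some patients. In general the estimate matches neither the effect regardless of increases nor the effect without them.

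The size and direction of bias cannot be determined from the documents. Under the assumptions shown, the shift from a 4-point no-increase effect is mostly a few tenths, in either direction, and it cannot be assumed conservative. Type I error inflation is not shown when the drug changes neither scores nor increase rates. This should be fixed because the defect sits in the primary analysis, not because of the simulated size.

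**What to change.** 1. Remove the score-based exclusion and make the SAP's ITT population primary for UPDRS-III. State that it still requires a dose and a post-baseline UPDRS-III or ADAS-Cog 11, so it is not all randomised patients. This step alone would give the treatment-policy result (3.27 at 40%/20%), so it needs step 2.
2. The rule appears intended to remove the influence of added anti-parkinsonian medication, so name the no-increase estimand as primary. Define the increase from medication records reviewed blind, without the Week 24 dose or score, and say how temporary increases count. Set UPDRS-III values after the increase to missing in the planned MMRM and state the missing-at-random assumption.
3. Add a delta-shift sensitivity analysis over a range. With the unobserved trigger at 40%/20%, a shift of about 3.5 points restores 4.0; the same shift in the first model gives 4.00 + 3.5 × (0.200 − 0.079) ≈ 4.4, so no single value serves.
4. Commit to the analysis of all observed ITT values as a named sensitivity analysis. Keep the current primary set and the UPDRS Sensitivity set as supportive only.
5. Give increases their own partial-date rule. SAP 7.7.3 would date an increase known only by year, if that is the year of first dose, to the first-dose day, and step 2 would then blank every post-baseline score.

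Cost: SAP and protocol wording and a blinded medication review; no new visits. Slightly more Week 24 values leave the model (20% against 18% of placebo at 40%/20%), though earlier scores stay in. Missing at random is hard to check across 20 weeks without a UPDRS-III visit. Some records may lack dose detail, because Protocol 7.9.1 requires at minimum only drug name and dates.
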